8.2 Subgroup Definition and Parameterization

The following factors, based on data collected on the eCRF, will be used as cofactors for all the stratified analyses:

- Treatment with corticosteroids therapy within 48 hours from randomization (as collected in the ‘Randomization’ eCRF page)
 - Corticosteroids dose \leq 15 mg of prednisone-equivalent (reference level)
 - Corticosteroids dose $>$ 15 mg of prednisone-equivalent

- Country
 - United States of America (reference level)
 - Philippines
 - Brazil

The following subgroups then, including the two stratification factors defined above and based on information collected at baseline, will be defined:

Comorbidities:

- Presence of obstructive lung disease (as collected in the ‘Medical History’ eCRF page)
 - No (reference level)
 - Yes

- Obesity based on BMI
 - No: Body Mass Index (BMI - derivation described at Section 11.1) $<$ 30 kg/m² (reference level)
 - Yes: BMI \geq 30 kg/m²

- Diabetes co-morbidity at study entry (as collected in the ‘Medical History’ eCRF page)
 - No (reference level)
 - Yes

- Heart diseases co-morbidity at study entry (as collected in the ‘Medical History’ eCRF page)
 - No (reference level)
 - Yes

- Hypertension co-morbidity at study entry (as collected in the ‘Medical History’ eCRF page)
 - No (reference level)
 - Yes

- Number of relevant comorbidities (derived for each participant counting the number of comorbidities among the ones listed above, including obesity based on BMI):
 - No (reference level)
 - Yes: 1 or 2
 - Yes: more than 2

Use of Relevant Therapies at baseline:

- Treatment with corticosteroids therapy within 48 hours from randomization (as collected in the 'Randomization' eCRF page)
 - Corticosteroids dose \leq 15 mg of prednisone-equivalent (reference level)
 - Corticosteroids dose $>$ 15 mg of prednisone-equivalent
- Treatment with antiviral therapy (AVT) including convalescent serum within 48 hours from randomization (as collected in the 'Randomization' eCRF page)
 - No (reference level)
 - Yes

Demographic characteristics:

- Age (derivation described at Section 11.1)
 - Age $<$ 60 (reference level)
 - Age \geq 60
- Gender
 - Male (reference level)
 - Female
- Ethnicity
 - Hispanic or Latino
 - Not Hispanic nor Latino (reference level)

Other characteristics:

- Country
 - United States of America (reference level)
 - Philippines
 - Brazil
- Site
- Smoking status at study entry (as collected in the ‘Substance Usage’ eCRF page)
 - Smoker (former, or regular tobacco use)
 - Non-Smoker (never used tobacco, reference level)

Subgroup analyses will be performed on primary and selected secondary efficacy endpoint as defined below. CCI

For the definition of subgroup level, data as documented in the eCRF will be taken. The category “missing” will not be included in any subgroup analysis.

For subgroups with two categories only, in case of less than 9 participants within each category the subgroup will not be considered for the analysis.

CCI

9 General Specifications for Data Analyses

This section describes any general specifications not included in subsequent sections.

Part A objectives will be separately described only in case of early termination of the study for safety reasons, otherwise all data from all study participants from Part A and Part B will be combined.

Study treatment groups are defined and labeled as Placebo, M5049 50 mg BID, and M5049 100 mg BID. Unless otherwise indicated, all tables will be presented by study treatment groups. For demographics, baseline and safety data a total column is also presented.

The “start date” for this study is the first dose date (Day 1).

Unless otherwise specified, comparisons will be presented for each dose of M5049 versus placebo.

In this study there will be no hypothesis testing; therefore, all statistical tests mentioned in this IAP are to be regarded as exploratory. Exploratory statistical tests comparing study treatment groups will be performed two-sided and confidence intervals (CI) will be two-sided with a confidence probability of 95%, unless otherwise specified in this IAP.

All analyses will be performed using SAS® Software Version 9.2 or higher, with the exception of M5049 PK parameters which will be derived using noncompartmental methods with the validated computer program PPD [REDACTED] or higher PPD [REDACTED].

9.1 Presentation of continuous and qualitative variables

Continuous variables other than PK will be summarized using the following descriptive statistics, i.e.

- number of subjects with non-missing values (n)
- mean, standard deviation

- median, 25th Percentile - 75th Percentile (Q1-Q3)
- minimum (Min) and maximum (Max)

Missing statistics, e.g. when they cannot be calculated, should be presented as “nd”. For example, if $n=1$, the measure of variability (SD) cannot be computed and should be presented as “nd”.

Qualitative variables will be summarized by counts and percentages.

Mean, median, Q1, Q3, Min, and Max will have the same precision as collected in SDTM datasets for non-derived data. Standard deviation will be presented with 1 digit more than the mean. Percentage and percent change from baseline will be reported using 1 decimal digit, if not specified otherwise.

Unless otherwise stated, the calculation of proportions will be based on the number of subjects in the analysis set of interest. Therefore, counts of missing observations will be included in the denominator and presented as a separate category.

For variables where a subject may have more than one category due to multiple responses per subject (i.e. not mutually exclusive categories), the number of subjects included in each category will be summarized as a percentage from all subjects. Therefore, the total frequency across categories may not equal the total number of all subjects in the population.

9.2 Presentation of Pharmacokinetic Results

9.2.1 Presentation of Pharmacokinetic Concentration Data

M5049 concentration data will be descriptively summarized using: number of non-missing observations (n), arithmetic mean (Mean), SD, coefficient of variation (CV%), minimum (Min), median (Median), and maximum (Max). In cases with $n \leq 2$, only n, Min, and Max will be reported.

Descriptive statistics of PK concentration data will be calculated using values with the same precision as the source data and rounded for reporting purposes only. The following conventions will be applied when reporting descriptive statistics of PK concentration data:

| | |
|-------------------------|----------------------|
| Mean, Min, Median, Max: | 3 significant digits |
| SD: | 4 significant digits |
| CV%: | 1 decimal place |

9.2.2 Presentation of Pharmacokinetic Parameter Data

Pharmacokinetic parameter data will be descriptively summarized using: n, Mean, SD, CV%, Min, Median, Max, geometric mean (GeoMean), the geometric coefficient of variation (GeoCV), and the 95% CI for the GeoMean (LCI 95% GM, UCI 95% GM). For time to reach maximum observed

concentration (t_{max}), only n, Min, Median, and Max will be reported. In cases with $n \leq 2$, only n, Min, and Max will be reported. The PK parameter maximum observed plasma concentration (C_{max}) will be reported with the same precision as the source data. All other PK parameters will be reported to 3 significant figures. In export datasets, as well as in the SDTM PP domain, PK parameters will be provided with full precision, and will not be rounded. Descriptive statistics of PK parameter data will be calculated using full precision values, and rounded for reporting purposes only.

The following conventions will be applied when reporting descriptive statistics of PK parameter data:

Mean, Min, Median, Max, GeoMean, 95% CI: 3 Significant digits

SD: 4 Significant digits

CV%, GeoCV%: 1 decimal place

9.3 Definition of Baseline and Change from Baseline

In general, the last non-missing measurement prior to first dose will serve as baseline measurement.

Unless otherwise specified, if a scheduled pre-dose measurement actually occurred post-dose, then the corresponding measurement will be analyzed similar to an unscheduled post-dose measurement.

Absolute and percent changes from baseline are defined as:

absolute change = analysis visit value – baseline value

percent change = $100 * (\text{analysis visit value} - \text{baseline value}) / \text{baseline value}$

9.4 Study Treatment Day

Day 1 is the day of first study drug administration, the day before is Day -1 (no Day 0 is defined). Study day is defined relative to Day 1.

9.5 Definition of Duration and ‘time since’ Variables

Durations in days will be calculated by the difference of start and stop date/time (e.g. survival time (days) = date/time of death – date/time of first dose) if not otherwise specified.

The time since an event (e.g. time since diagnosis) will be calculated as reference date/time minus date/time of event, when available.

9.6 Conversion Factors

The following conversion factors will be used to convert days into months or years:

1 week = 7 days, 1 month = 30.4375 days, 1 year = 365.25 days.

If height is recorded in inches, height (cm) = height (in) × 2.54.

If weight is recorded in pounds, weight (kg) = weight (lbs) ÷ 2.2046.

9.7 Definition of On-treatment Period

The on-treatment period is defined as any time on or after the first dose of study treatment.

The on-treatment period ends with the date of last contact or death, whichever occurs first.

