Routine hematology, chemistry	X	←---Once daily during hospitalization (incl. predose on Day 1). If discharged, then at study visits (e.g., Days 3, 5, 7, 10, 14, 21, 28) if participant returns to study site-----→													WBC with differential: numbers and percentage, Hgb, HCT, platelets; electrolytes, BUN, Cr, eGFR, albumin, glucose, TP, ALT, AST, CK (unless participant is discharged). See Appendix 4 . Labs obtained within 24 hours of Day 1 can be used for Day 1 assessments. Record results daily from the participant's chart (unless participant is discharged). Evaluations to be performed by local laboratory.
Inflammatory biomarkers tested in COVID-19 (CRP, d-dimer, and ferritin)	X	X		X		X	X	X	X		X			X	Record any available results (and time sample collected) from the participant's chart on days indicated (unless participant is discharged). Part A and Part B: Evaluations to be performed by local laboratory.

Assessments and Procedures	SCR	Intervention Period (Days)							Continued Surveillance		Safety Follow-up			Relapse Admission ^a	Notes
									HD/ET	EoT					
	(up to 48 hours before Day 1)														HD assessments should occur if participant discharged after Day 3 and before Day 14. ET (early termination of treatment) Visit should occur within + 24 hours of treatment discontinuation.
Study Day		1	2	3	5	7	10		14	21	28	44	60	5 to 60	
Visit Window			± 6 h		± 12 h		± 24 h			+ 2 days		± 5 days	± 7 days	± 6 h	
Predose PK		X		X		X									PK blood collection must be done within 60 minutes prior to dose administration. Identify and record the time of the closest meal consumed prior to the study intervention administration, i.e., when the last meal was finished before the study intervention administration (unless participant is discharged). PK evaluations to be performed by central laboratory.

Assessments and Procedures	SCR	Intervention Period (Days)							Continued Surveillance		Safety Follow-up			Relapse Admission ^a	Notes
		1	2	3	5	7	10	HD/ET	EoT	21	28	44	60		
	(up to 48 hours before Day 1)														HD assessments should occur if participant discharged after Day 3 and before Day 14. ET (early termination of treatment) Visit should occur within + 24 hours of treatment discontinuation.
Study Day		1	2	3	5	7	10		14	21	28	44	60	5 to 60	
Visit Window			± 6 h	± 12 h	± 24 h					+ 2 days	± 5 days	± 7 days	± 6 h		

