5.2 Part B Objectives

| OBJECTIVES | ENDPOINTS (OUTCOME MEASURES) | IAP SECTIONS |
|---|--|---|
| Primary Efficacy | | |
| To evaluate the time to recovery in participants hospitalized due to COVID-19 pneumonia with M5049 compared to placebo. | Time to recovery from Day 1 through Day 28, defined as time from Day 1 to first occurrence of WHO 9-point ordinal scale 3 or less. | 14.1 |
| Primary Safety | | |
| To assess the safety of M5049 compared to placebo. | 
 Incidence of TEAEs, AESIs, TEAEs leading to treatment discontinuation, and SAEs from Day 1 through Day 60. Clinically significant changes in laboratory parameters and ECGs from Day 1 through Day 28. | 
 15.1 15.3 and 15.5 |
| Secondary | | |
| To assess the proportion of participants free of respiratory support with M5049 compared to placebo. | Alive and not requiring supplemental oxygenation (including any supplemental oxygen, noninvasive or mechanical ventilation and ECMO) through Day 28. | 14.2.1 |
| To evaluate the change in clinical status with M5049 compared to placebo. | 
Clinical status from Day 1 through Day 60 (on a 9-point ordinal scale):
 
 0. Uninfected: no clinical or virological evidence of infection. 1. Ambulatory: no limitation of activities. 2. Ambulatory: limitation of activities. 3. Hospitalized, mild disease: hospitalized, no oxygen therapy. 4. Hospitalized, mild disease: oxygen by mask or nasal prongs. 5. Hospitalized, severe disease: noninvasive ventilation or high flow-oxygen. 6. Hospitalized, severe disease: intubation and mechanical ventilation. 7. Hospitalized, severe disease: ventilation + additional organ support – e.g., pressors, RRT, ECMO. 8. Death. | 14.2.2 |
| To assess normalization of oxygenation status with M5049 compared to placebo in participants who are alive and not on mechanical ventilation. | 
Time to SpO₂ of ≥ 94% sustained for at least 24 hours in room air from Day 1 through Day 28.
 
Further referred as “time to SpO₂ improvement”
 | 14.2.3 |

| OBJECTIVES | ENDPOINTS (OUTCOME MEASURES) | IAP SECTIONS |
|---|--|--|
| To evaluate the numbers of deaths with M5049 compared to placebo. | All-cause mortality (Day 1 through Day 60). | 14.2.4 |

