9.9 Analysis visit windows

For endpoints to be reported by visit, the following analysis visit windows will be defined:

- Baseline (see Section 9.3 for definition)
- Analysis Day 2
- Analysis Day 3
- Analysis Day 4
- Analysis Day 5: Day 5 and 6
- Analysis Day 7: Day 7 and 8
- Analysis Day 10: from Day 9 to Day 11
- Analysis Day 14: from Day 12 to Day 17
- Analysis Day 21: from Day 18 to Day 24
- Analysis Day 28: from Day 25 to Day 35
- Analysis Day 44: from Day 36 to Day 52
- Analysis Day 60: from Day 53 onwards

In case of multiple assessments collected within the same window, the one closest to the target date will be used for summary statistics. All the assessments will be used for worst case analyses.

10 Study Participants

The subsections in this section include specifications for reporting participant disposition and study treatment/study discontinuations. Additionally, procedures for reporting protocol deviations are provided.

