15.3 Clinical Laboratory Evaluation

Clinical laboratory evaluation will be collected on the 'Local Laboratory Results: Hematology' and 'Local Laboratory Results: Chemistry' eCRF pages.

Laboratory values (including corresponding normal ranges) from the local labs will be used for summary statistics and shift tables.

Quantitative laboratory parameters reported as "< X", below the lower limit of quantification (BLQ), "> X" or above the upper limit of quantification (ULQ), will be converted to X/lower

limit/upper limit for the purpose of quantitative summaries (with the exception of eGFR), but will be presented as recorded, i.e. as “< X”, BLQ, “> X” or ULQ in listings.

The full list of parameters with NCI-CTCAE grades available and not available and relevant directions of abnormalities of interest are listed in Appendix 1 at section 18.1.

Laboratory results will be classified according to the NCI-CTCAE criteria version 5.0. Some of the toxicity gradings are based on laboratory measurements in conjunction with clinical findings. Non-numerical qualifiers will not be taken into consideration in the derivation of CTCAE criteria (e.g., hypokalemia Grade 1 and Grade 2 are only distinguished by a non-numerical qualifier and therefore Grade 2 will not be derived).

Additional laboratory results that are not part of NCI-CTCAE will be presented according to the categories: below normal limit, within normal limits and above normal limit (according to the laboratory normal ranges).

For estimated glomerular filtration rate (mL/min/1.73 m²) the value collected in CRF will be used when reported. When missing or reported as “>/<X”, it will be calculated using the Modification of Diet in Renal Disease equation:

$$\text{eGFR} = 175 \times (\text{serum creatinine in mg/dL})^{-1.154} \times (\text{age in years})^{-0.203} \times 0.742 \text{ (if female)} \times 1.212 \text{ (if race is black)}$$

The following summaries will be provided by treatment group for each of chemistry and

hematology laboratory:

All parameters:

- Summary results based on normal ranges by time points will include number and percentage of participants below normal limit, within normal limits and above normal limit.

Non-gradable parameters according to NCI-CTCAE:

- Shift from baseline to the worst on-treatment value according to normal range criteria

Gradable parameters according to NCI-CTCAE:

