- Shift from baseline to the worst on-treatment value for each relevant directionality (minimum and/or maximum value) according to the CTCAE toxicity grades; the highest CTCAE grade during the on-treatment period is considered as the worst grade for the summary
- Summary results based on CTCAE grade by time point will include number and percentage of participants with Grade 1, 2, 3, 4, 3/4, and any grade (1 to 4).

For those parameters which are graded with two directions of toxicities such as potassium (hypokalemia/hyperkalemia), the toxicities will be summarized separately. Low direction toxicity (e.g., hypokalemia) grades at baseline and post baseline will be set to 0 when the variables are derived for summarizing high direction toxicity (e.g., hyperkalemia), and vice versa.

Spaghetti plots for Aspartate Aminotransferase, Alanine Aminotransferase and Total Bilirubin, will be presented by treatment group, including only those participants with any NCI CTCAE grade 2 or higher at any point in time during the study.

The listings of laboratory results will be provided for all laboratory parameters. The listings will be sorted by actual treatment, then subject ID, parameters and assessment dates for each participant. Laboratory values that are outside the normal range will also be flagged in the data listings, along with corresponding normal ranges and CTCAE grades. A listing for laboratory normal ranges will also be provided.

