15.5 Other Safety or Tolerability Evaluations

ECG data will be collected on the 'ECG' eCRF page.

ECG summaries will include all ECG assessments from the on-treatment period.

The analysis of QT data is complicated by the fact that the QT interval is highly correlated with heart rate. Because of this correlation, formulas are routinely used to obtain a corrected value, denoted QTc, which is independent of heart rate. This QTc interval is intended to represent the QT interval at a standardized heart rate. Several correction formulas have been proposed in the literature. For this analysis we will use some of those methods of correction, as described below. The QT interval corrected for heart rate by the Fridericia's formula, QTcF, is defined as

$$QTcF = \frac{QT}{\sqrt[3]{RR}},$$

where RR represents the RR interval of the ECG, in seconds, and can be estimated as 60/Heart Rate.

QTcF values collected in the eCRF will be used for the analysis. In case those are missing, this parameter will be derived based on RR and QT.

The following analyses will be performed for each of the applicable ECG parameters (ventricular rate, denoted as HR in what follows, PR, RR, QRS, QT, QTc and QTcF) by treatment group, during the on-treatment period. Unscheduled ECG measurements will not be used in computing the descriptive statistics for change from baseline at each post-baseline time point. However, they will be used in the analysis of notable ECG changes.

- For each of the ECG parameters (HR, PR, RR, QRS, QT, QTc and QTcF), descriptive statistics of absolute and changes from baseline values at scheduled time points will be reported.
- Shift to worst post-baseline investigator interpretation.
- Shift to worst post-baseline value according to the notable ECG categories presented below. Maximum post-baseline value will be used.
 - QTcF increase from baseline >30 ms, >60 ms
 - QTcF > 450 ms, > 480 ms, > 500 ms

Complete ECG profiles will be listed, and notable ECG interval value or change will be flagged.

16 Analyses of Other Endpoints

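### The worst-value laboratory and ECG tables run to last contact, although the primary safety endpoint they report closes at Day 28

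*SAP*

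**What the plan says.** SAP 5.2 gives the second part of the primary safety endpoint as "Clinically significant changes in laboratory parameters and ECGs from Day 1 through Day 28". SAP 5.1 and protocol sections 3.1 and 3.2 use the same window. The SAP objectives table points this endpoint to sections 15.3 and 15.5.

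Those sections use another window:

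- SAP 15.3, non-gradable laboratory parameters: "Shift from baseline to the worst on-treatment value according to normal range criteria".
- SAP 15.3, gradable parameters: "the highest CTCAE grade during the on-treatment period is considered as the worst grade for the summary".
- SAP 15.5: "ECG summaries will include all ECG assessments from the on-treatment period", followed by "Shift to worst post-baseline value according to the notable ECG categories presented below". Unscheduled tracings are kept out of the scheduled change-from-baseline statistics but admitted to the notable-change analysis.

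SAP 9.7 starts the on-treatment period at first dose and closes it late: "The on-treatment period ends with the date of last contact or death, whichever occurs first". SAP 9.9 adds that "All the assessments will be used for worst case analyses". Neither 15.3 nor 15.5 contains a Day 28 limit. SAP section 7, which lists departures from the protocol analyses, deals only with stratification factors.

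**The concern.** A rule that takes each participant's worst value over a longer period than the endpoint allows reports something other than the endpoint. A Day 50 value would enter the main shift table for an endpoint that closed on Day 28.

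The extra days are also not observed evenly. A maximum taken over more days and more tests can only stay the same or rise, and after Day 28 the extra tests fall mainly on people who are still in hospital, have been readmitted, or have a clinical reason for an ECG. Whether a participant contributes late values is therefore partly an outcome of the trial. Protocol section 7.4 also lifts drug restrictions after Day 28, so a late laboratory or QTc abnormality can have causes that the protocol no longer limits.

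The tables affected are the ones a reader would turn to first for individual worst changes: laboratory shift to worst, worst CTCAE grade, and notable QTcF.

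**Working it through.** The plan gives no figure for this point. The check traces the definitions and does window arithmetic.

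**1. Which outputs are affected**

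| Output | Window as written | Matches Day 1 to 28? |
|---|---|---|
| Laboratory shift to worst, non-gradable (15.3) | first dose to last contact or death | No |
| Laboratory shift to worst grade, gradable (15.3) | first dose to last contact or death | No |
| ECG shift to worst and notable ECG (15.5) | post-baseline, on-treatment | No |
| Laboratory and ECG summaries by time point | labelled by visit | Not affected; a reader can stop at Day 28 |
| TEAEs (15.1) | on-treatment period | Endpoint runs to Day 60, so the long period fits |

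A single definition serves two endpoints. It suits the adverse event part (Day 60) but not the laboratory and ECG part (Day 28).

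**2. Size of the mismatch in days**

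- Endpoint window: 28 days. Analysis window for a completer: about 60 days.
- Excess: 60 − 28 = 32 days; 32/60 = 53%.
- If the last visit may be 7 days late (one reading of the visit-window row in Table 1): 67 − 28 = 39 days; 39/67 = 58%.

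**3. Relation to dosing**

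Dosing lasts 14 days, and protocol section 4.3 gives a half-life of 7 to 11 hours. Five half-lives are 5 × 7 = 35 to 5 × 11 = 55 hours, or 1.5 to 2.3 days. The on-treatment label thus continues for about six weeks after the drug has largely cleared.

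**4. Who supplies values after Day 28**

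- Laboratory tests (protocol Table 1): "Once daily during hospitalization (incl. predose on Day 1"; the visits listed for discharged participants stop at Day 28. The wording sets no Day 28 limit for inpatients. The layout of this row is broken in the text I worked from, so the formatted table should be checked for where its arrow ends and whether it covers the relapse column.
- ECGs: the last scheduled tracing is at Day 28, but clinically indicated tracings are kept whenever they occur. Late ECGs are clearly eligible.
- Protocol section 4.7 expects Day 44 and Day 60 contacts by telemedicine or phone, which yield no routine laboratory or ECG data.

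**5. Illustration of scale (all rates assumed; none is in the documents)**

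Let p be the share already counted by Day 28, f the share in hospital or readmitted afterwards, and q the chance that such a participant first reaches a notable value then. The added share is (1 − p) × f × q. There are about 150/3 = 50 participants per arm.

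- Low: p = 40%, f = 5%, q = 25%: 0.60 × 0.05 × 0.25 = 0.0075, or 0.75 points, 0.4 participants.
- High: p = 20%, f = 20%, q = 50%: 0.80 × 0.20 × 0.50 = 0.08, or 8 points, 4 participants.

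For comparison, the standard error of a difference between two arms at a 20% rate is √(2 × 0.2 × 0.8/50) = 8.0 points.

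**The case against.** The strongest reply is that this is a wording mismatch with little effect. By-visit summaries already show the data through Day 28. Listings carry assessment dates, flags and grades, so late values can be picked out. SAP section 9 calls all tests exploratory, and including all follow-up is a cautious habit in safety reporting. The volume of late laboratory data is uncertain: the vital-sign and oxygen-saturation rows of Table 1 use similar in-hospital wording and appear to stop at Day 28, and the laboratory row may do the same.

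Much of this stands. It narrows the point to the worst-value tables and leaves late ECGs as the firmer case. It does not remove the mismatch, because a by-visit summary does not give each participant's worst change within the endpoint window.

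Three stronger readings are tempting, and the documents do not support them.

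- A reader might infer that late values cannot reflect the drug. Clearance within about two days makes concurrent exposure unlikely but does not exclude delayed effects. The same argument would discard roughly Days 17 to 28, which the endpoint keeps.
- A reader might project the number in hospital at Day 28 from the median recovery times of 7 to 10 days quoted in the protocol's amendment rationale: 2^(−27/7) = 0.069 and 2^(−27/10) = 0.154, or about 3 to 8 of 50. Those medians come from another trial, and the exponential shape is assumed. Recovery on this scale includes inpatients off oxygen, and deaths count as unrecovered but yield no late values.
- A reader might infer a bias for or against a dose. A rise common to all arms is not a bias between arms, and nothing in the documents gives long stays or readmissions by arm.

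Uneven testing also exists before Day 28, since inpatients are tested daily and discharged participants only at visits. Correcting the window does not cure that.

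**Conclusion.** The point holds for the laboratory shift-to-worst and worst-grade tables and for the ECG shift-to-worst and notable-ECG tables. As written, they compute worst values over about 60 days for an endpoint defined over 28, with up to 32 days (53%) outside it and no declared change. This follows from the text and needs no assumed rate.

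The practical effect is uncertain. The range of 0.4 to 4 participants per arm rests wholly on assumed rates and shows only that the effect could be anything from negligible to visible in an arm of 50. Neither the size nor the direction of a between-arm effect can be derived. The correction should be made before database lock because it is cheap and concerns a primary safety endpoint, not because a distortion has been shown.

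**What to change.** In SAP 15.3 and 15.5, state that the shift-to-worst, worst-grade and notable-ECG tables use assessments from first dose through Day 28, and that a scheduled Day 28 visit held late still counts if it falls within the SAP 9.9 window for Analysis Day 28 (Days 25 to 35). A bare calendar cut at Day 28 would discard valid planned visits. Show later laboratory and ECG values in a separate summary or listing. Leave SAP 9.7 and the Day 60 window for TEAEs as they are. If the sponsor prefers the longer window, it should be declared and justified in SAP section 7.

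The cost is about one sentence in each of the two sections, a date filter with a rule for the late Day 28 visit, and one extra display. The downside is that late abnormalities leave the main tables. They remain visible in the separate display and, if clinically important, as TEAEs through Day 60.
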